#### 7.2.3.4.4. ACT total score of $\geq 20$ and/or an increase from baseline of $\geq 3$ in ACT total score at Month 6 (Visit 10).

Endpoint
Percentage of patients who have either an ACT total score of $\geq 20$ and/or an increase from baseline of $\geq 3$ in ACT total score at Month 6 (Visit 10).
Model Specification
This endpoint will be analysed using a logistic regression model. Only the month 6 (visit 10) data will be included in the model. Month 1 (visit 5) data will not be implemented since by this timepoint participants may not have reverted to steady medicating behaviour.
Terms in the model: 
 
Dependent variable: Composite ACT total score <math>\geq 20</math> and/or increase from baseline of <math>\geq 3</math> in ACT total score at month 6 responder/non-responder (binary score)
 
Covariates: 
 
Categorical: randomised treatment arm, gender and country
 
Continuous: baseline ACT total score and age.
 
 
 
 Patients who have a missing ACT total score at month 6 (visit 10) (i.e. no ACT data on-treatment) will be classified as non-responders at that visit.
Computation of confidence intervals for the odds ratios is based in the individual Wald tests.
Model Checking & Diagnostics
If the likelihood maximisation algorithm fails to converge due to complete or quasi-complete separation of the data then Firth's penalized likelihood (Firth, 1993) will be implemented by use of the FIRTH option on the MODEL statement in PROC LOGISTIC.
The fit of the logistic regression model will be assessed by examining the ROC curve and other diagnostic plots.
Model Results Presentation
The number and percentage of participants with a response within each randomised treatment arm will be presented by visit, together with the adjusted odds ratio comparing CIS Arms 1, 2, 3, 4 with Arm 5, associated 95% CIs and p-values.

### 7.3. Exploratory and Other Analyses

The impact of the HCP having access to sensor data on percentage of ELLIPTA doses taken (daily adherence) between the beginning of month 4 and the end of month 6 as determined by the maintenance sensor will be assessed by the following comparisons:

- Arm 1 vs Arm 2

- Arm 3 vs Arm 4

The impact of having Rescue Medication data being available on the percentage of ELLIPTA doses taken (daily adherence) between the beginning of month 4 and the end of month 6 as determined by the maintenance sensor will be assessed by the following comparisons:

- Arm 1 vs Arm 3
- Arm 2 vs Arm 4

These estimates will be generated from the multiple imputation analysis used to assess the primary endpoint.

The effect of 6 months use with CIS on health care utilisation will be explored as well as its effect on the following patient reported outcomes (PROs); asthma system utility index (ASUI), St. Georges Respiratory Questionnaire (SGRQ), Patient Activation Measure (PAM), Medication Adherence Report Scale for Asthma (MARS-A), Beliefs in Medicine Questionnaire (BMQ).

The reliability and usability of the CIS, as well as the impact of the adherence on Fractional exhaled nitric oxide (FeNO) and Peak Expiratory Flow (PEF) will be assessed.

### **7.3.1. Exploratory ELLIPTA Adherence Measure Analyses**

#### **7.3.1.1. Endpoint**

The percentage of ELLIPTA doses taken (daily adherence) between the beginning of Month 4 and the end of Month 6 as determined by the maintenance sensor. Daily adherence is defined as the participant taking one dose of Relvar/Breo ELLIPTA, within a 24-hour period, starting at 12.00am each day of the run-in and treatment period

#### **7.3.1.2. Summary Measure**

The mean difference in daily adherence between the comparisons of interest will be estimated from an Analysis of Covariance (ANCOVA) model allowing for effects due to randomised treatment, baseline adherence, duration of run-in (visits), country, gender, and age (years).

#### **7.3.1.3. Population of Interest**

The exploratory adherence analyses will be based on the Intent-To-Treat population.

#### **7.3.1.4. Strategy for Intercurrent (Post-Randomisation) Events**

The steps detailed in Section 7.1.4 Strategy for Intercurrent (Post-Randomisation) Events will be applied sequentially when deriving the secondary adherence endpoints. See Section 10.5.3.1 ELLIPTA Device Sensor Assessments for further derivation details.

#### **7.3.1.4.1. Events prior to premature discontinuation of the ELLIPTA maintenance sensor**

The treatment policy estimand is directly assessed using the observed adherence data while the ELLIPTA maintenance sensor is in use, regardless of whether the CIS feedback is discontinued.

Any missing intermittent adherence data will be imputed as non-adherent i.e. the participant will be assumed to have not taken their treatment within the 24-hour time period/window, where there is no evidence of device or technical/transmission failure.

Missing intermittent adherence data due to a medical device incident such as device failure, technical failure of the sensor, or data transmission failure will be assumed to be missing at random (MAR). For each participant, the percentage adherence measure will be calculated from the proportion of the number of days a participant is adherent divided by the number of days data provided in that month.

#### **7.3.1.4.2. Events following premature discontinuation of the ELLIPTA maintenance sensor**

It is assumed that participants would continue to take ELLIPTA as they would have without the CIS intervention (J2R imputation) following discontinuation of the ELLIPTA maintenance sensor.

It is assumed that ELLIPTA treatment is no longer appropriate if the participant discontinues ELLIPTA but remains in the study or withdraws for a reason related to ELLIPTA. The ELLIPTA adherence endpoint is no longer considered relevant and subsequent follow-up is excluded from the analysis, with participants weighted in the analysis by the proportion of months 4 to 6 for which data is included.

It is assumed that participants would continue to take ELLIPTA as they would have with their allocated CIS intervention (MAR imputation) following concurrent discontinuation of the ELLIPTA maintenance sensor and withdrawal unrelated to ELLIPTA or CIS.

#### **7.3.1.5. Statistical Analyses / Methods**

Details of the planned displays will be provided in Section 10.8, [Appendix 8: List of Data Displays](#) and will be based on GSK data standards and statistical principles.

Unless otherwise specified, endpoints /variables defined in Section 7.3.1.1 Endpoint will be summarised using descriptive statistics, graphically presented (where appropriate) and listed.

### 7.3.1.6. Statistical Analyses / Methodology Specification

#### 7.3.1.6.1. *The percentage of ELLIPTA doses taken (daily adherence) between the beginning of Month 4 and the end of Month 6*

Endpoint / Variables

The percentage of ELLIPTA doses taken (daily adherence) between the beginning of Month 4 and the end of Month 6 as determined by the maintenance sensor for the following treatment arm comparisons:
 
 
• HCP having access to sensor data 
 
• Arm 1 vs Arm 2
 
• Arm 3 vs Arm 4
 
 
 
• Rescue medication data being available 
 
• Arm 1 vs Arm 3
 
• Arm 2 vs Arm 4
 
 
 
 
Daily adherence is defined as the participant taking one dose of Relvar/Breo ELLIPTA within a 24-hour period, starting at 12.00am each day of treatment period.

Multiple Imputation Specification

Imputation will be carried out using monthly adherence rates for months 1 to 6. 1000 draws will be used. For each draw, four intermediate imputation datasets will be created to allow for the handling of fully unobserved months (using set A imputations) and partially unobserved months (using set B imputations).
 
 
• Set A where the partially observed month is directly estimated under the MAR assumption as the proportion of the number of days a participant is adherent divided by the number of days data provided in that month. 
 
• J2R imputations
 
• MAR imputations
 
 
 
• Set B where the partially observed month is set to missing. 
 
• J2R imputations
 
• MAR imputations
 
 
 
 
The timing of the intercurrent events of discontinuation of the ELLIPTA maintenance sensor, discontinuation of ELLIPTA and withdrawal from study will be used to identify the proportion of each month to be assigned as observed data, J2R imputed data, MAR imputed data, or no data. The strategy for handling intercurrent events is described in Section 7.1.4 Strategy for Intercurrent (Post-Randomisation) Events.
 
Within each imputation draw, for each month, the observed and any imputed data will be combined to provide a percentage adherence value. The values for months 1 to 6 will be combined to create the value

for the secondary analysis and the weight to be assigned to each participant.

Multiple imputation using Rubin's rules will be used to estimate the treatment effect and associated standard error, by performing the ANCOVA analysis described below on the secondary endpoint within each dataset.

The multiple imputation will be implemented using the methods described in Carpenter, 2013, using the macros available from <https://missingdata.lshtm.ac.uk/2017/04/06/gsk-five-macros/>.

#### Model Specification

The analysis will be performed on the percentage adherence between Months 4 and 6 using an Analysis of Covariance (ANCOVA) model allowing for effects due to randomised treatment arm, baseline adherence, duration of run-in (visits), country, gender, and age (years).

Baseline adherence will be the percentage ELLIPTA doses taken (daily adherence) during the last 28 days of the run-in period prior to randomisation. Randomised treatment, duration of run-in (visits), country, and gender will be included as categorical covariates; baseline adherence and age (years) will be included as continuous covariates.

Each participant will be weighted by the proportion of months 4 to 6 for which data is included in the percentage adherence endpoint (both observed and imputed data are accounted for in the weighting).

Data from five individual CIS treatment arms will be included in the model, and used to estimate the difference between:

- Arm 1 and Arm 2
- Arm 3 and Arm 4
- Arm 1 and Arm 3
- Arm 2 and Arm 4

#### Model Checking & Diagnostics

Normality assumptions underlying the ANCOVA model used for analysis will be examined in a limited number of imputed datasets by obtaining a normal probability plot of the residuals and a plot of the residuals versus the fitted values (i.e. checking the normality assumption and constant variance assumption of the model respectively) to gain confidence that the model assumptions are reasonable.

If there are any departures from the distributional assumptions, alternative models may be explored using appropriately transformed data.

Interactions with treatment will be explored for other model covariates and tests for interactions will be at the 2-sided 10% significance level. Any significant interactions that are found will be thoroughly investigated and where necessary, extra outputs will be produced.

#### Model Results Presentation

Summary statistics (mean, standard deviation, median, minimum, maximum) of the primary endpoint will be provided, based on the observed percentages.

The adjusted means for each treatment arm and the estimated treatment arm difference for the treatment arm comparisons of interest will be presented together with the 95% confidence interval for the differences

and corresponding p-values from the multiple imputation procedure.

### 7.3.2. Exploratory Health Care Utilization Analyses

#### 7.3.2.1. Endpoints

- Number of outpatient visits relating to asthma
- Number of primary care visits relating to study HCP dashboard review (for relevant study arms)
- Number of and duration of hospitalisations, and ER visits due to asthma
- Annualised rate of severe exacerbations
- Number of unscheduled visits to primary care related to Asthma

#### 7.3.2.2. Population of Interest

The exploratory analyses will be based on the Intent-To-Treat population.

Endpoint
Healthcare Utilisation - 
 
• Number of outpatient visits relating to asthma
 
• Number of and duration of hospitalisations, and ER visits due to asthma
 
• Number of unscheduled visits to primary care related to Asthma
 

Summary

 
• The number and percentage of participants by frequency of unscheduled healthcare resource contacts (0, 1, 2, 3, 4, >4) will be summarized by contact type and treatment arm to characterize the level of healthcare associated with an asthma exacerbation. The frequency counts for each participant will be the total sum of contacts (or days in hospital) by type.
 
• The following types of healthcare contact for an exacerbation are recorded in the eCRF: 
 
• Number of telephone calls
 
• Number of home/day visits
 
• Number of home/night visits
 
• Number of physician office/practice visits
 
• Number of urgent care/outpatient visits
 
• Number of emergency room visits
 
• Number of inpatient hospitalisation days
 
• Number of contacts due to an exacerbation
 
 
 

Endpoint
Healthcare Utilisation -

 
Number of primary care visits relating to study HCP dashboard review (for relevant study arms)
 

Summary

 
The number and percentage of participants by frequency of unscheduled healthcare resource contacts (0, 1, 2, 3, 4, >4) will be summarized by contact type and treatment arm to characterize the level of healthcare associated with an asthma exacerbation. The frequency counts for each participant will be the total sum of contacts (or days in hospital) by type.
 

Endpoint
Healthcare Utilisation -

 
Annual rate of severe asthma exacerbations
 

Summary

 
The number and percentage of participants reporting an asthma exacerbation (on-treatment and post-treatment) will be summarised by treatment arm.
 
The number and percentage of participants with each number of exacerbations (0, 1, 2, 3, 4, >4) and the total number of exacerbations per treatment arm will also be summarised.
 
For the purposes of summarizing these data, the annualized rate of severe asthma exacerbations for the ITT population will be calculated for each participant as 
 
the number of exacerbations / time on Relvar/Breo (in years) from randomisation.
 
 
 
The summaries will include on-treatment exacerbations, from randomisation date to min(stop date of exposure + 1 day, date of study discontinuation).
 
The number and percentage of participants with an exacerbation that led to withdrawal of study, hospitalization, systemic/oral corticosteroids/antibiotics/medication being taken, or emergency room visit will be summarised by treatment arm.
 
A listing of severe exacerbations will be provided.
 

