## 5. STUDY DESIGN

### 5.1. Overall Design

Figure 2 : Study Schematic

This is an open-label, randomised, multi-centre, parallel group study consisting of 5 treatment arms, in asthmatic patients currently on a fixed dose ICS/LABA maintenance therapy.

The procedures to be performed at each visit are shown in Section 2. The study and visits are described here.

At all visits will require subjects to withhold a daily dose of maintenance therapy and rescue medication for 6 hours; as some assessments will require this restriction for validity of the assessment (PEF and FeNO) and also so correct use can be demonstrated with that day's Relvar/Breo ELLIPTA dose at any required visit.

The treatment period for the study is 6 months. However, due to the flexible run in period a subject could be on the study for approximately 7, 8 or 9 months in total

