## **11.2. Sample Size Determination**

### **11.2.1. Sample Size Assumptions**

The fixed sample size calculation is based on the primary endpoint, percentage of ELLIPTA doses taken (daily adherence) between Months 4 and 6 as determined by the maintenance sensor and has approximately 90% power to detect an absolute difference of 15% in the primary comparison. The treatment difference is based on the limited published data [[Charles](#), 2007, [van Boven](#), 2016]. This assumes a conservative standard deviation of 28% (based on a previous study [[Charles](#), 2007]) and significance declared at the two-sided 5% level.

Approximately 432 patients will be randomised in order to obtain at least 380 subjects (i.e. 76 subjects per arm) with available data over the last three months of the treatment period, in anticipation of a 12% drop-out within the first three months. Subjects will be randomised to one of five treatment arms with a ratio of 1:1:1:1:1.

Using the above assumptions the smallest observed effect predicted to result in a statistically significant difference between treatment groups is 9% (minimum detectable difference).

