
 
• Relvar/Breo on-treatment start date will be defined as the randomisation date and Relvar/Breo Treatment Stop Date will be defined as the latest treatment stop date (from the study treatment compliance eCRF log and treatment discontinuation eCRF page) for the participant. These dates will be used to determine whether a measurement is run-in, on or post-treatment. (See Section 10.3.1 Study Phases). Study conclusion is defined as completion or withdrawal, as applicable.
 
• Duration of exposure to study drug will be calculated as: 
 
◦ Duration of Exposure (days) = Treatment Stop Date – Randomisation Date + 1
 
 
 
• Duration of post-treatment time spent in the study will be calculated as: 
 
◦ Duration of Post-Treatment Study Time (days) = Study Conclusion Date – Treatment Stop Date
 
 
 
• Duration of total time spent in the study will be calculated as: 
 
◦ Duration of Study Time (days) = Study Conclusion Date – Randomisation Date + 1
 
 
 
• Years exposed will be calculated as: 
 
◦ Last treatment stop date - Randomisation Date + 1 / 365.25.
 
◦ Total Years Exposed will be the sum of the year exposed per treatment arm.
 
 
 
	

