Requiring use of systemic/oral corticosteroids	xx (xx%)					
Leading to hospitalisation	xx (xx%)					
Requiring emergency room visit	xx (xx%)					
No. of subjects with exacerbations requiring intubation	xx (xx%)					
No. of subjects with exacerbations leading to withdrawal from study	xx (xx%)					
Annual severe asthma exacerbation rate [1]						
n	XX	XX	XX	XX	XX	XX
Mean	XX.X	XX.X	XX.X	XX.X	XX.X	XX.X
SD	X.XX	X.XX	X.XX	X.XX	X.XX	X.XX
Median	XX.X	XX.X	XX.X	XX.X	XX.X	XX.X
Min.	XX	XX	XX	XX	XX	XX
Max.	XX	XX	XX	XX	XX	XX

[1] Summary only includes exacerbations for which a date of onset and resolution were provided in the eCRF..

Example EFF\_T1  
 Protocol : 207040  
 Population : Intent-to-Treat

Page 1 of 1

Table 2.xx  
 Summary of Asthma Symptom Utility Index (ASUI) Score

Visit		Arm 1 (N=xxx)	Arm 2 (N=xxx)	Arm 3 (N=xxx)	Arm 4 (N=xxx)	Arm 5 (N=xxx)
Baseline [1]	n	XX	XX	XX	XX	XX
	Mean	XX.X	XX.X	XX.X	XX.X	XX.X
	SD	X.XX	X.XX	X.XX	X.XX	X.XX
	Median	XX.X	XX.X	XX.X	XX.X	XX.X
	Min.	XX	XX	XX	XX	XX
	Max.	XX	XX	XX	XX	XX
Visit 5 (Month 1)	n	XX	XX	XX	XX	XX
	Mean	XX.X	XX.X	XX.X	XX.X	XX.X
	SD	X.XX	X.XX	X.XX	X.XX	X.XX
	Median	XX.X	XX.X	XX.X	XX.X	XX.X
	Min.	XX	XX	XX	XX	XX
	Max.	XX	XX	XX	XX	XX
Change from Baseline at Visit 5 (Month 1)	n	XX	XX	XX	XX	XX
	Mean	XX.X	XX.X	XX.X	XX.X	XX.X
	SD	X.XX	X.XX	X.XX	X.XX	X.XX
	Median	XX.X	XX.X	XX.X	XX.X	XX.X
	Min.	XX	XX	XX	XX	XX
	Max.	XX	XX	XX	XX	XX

[1] Baseline ASUI total score is taken at randomisation visit.

Programming note: repeat, Visit 10 (Month 6), Change from Baseline at Visit 10 (Month 6), Early Withdrawal

Example EFF\_T16

Protocol : 207040

Population : Intent-to-Treat

Page 1 of 1

Table 2.xx

Summary of Statistical Analysis of Percentage of Subjects Meeting a Responder Threshold of 0.09 Points Improvement (Increase) from Baseline (Randomisation) for the ASUI Total Score at Visit 10 (Month 6)

	Arm 1 (N=xxx)	Arm 2 (N=xxx)	Arm 3 (N=xxx)	Arm 4 (N=xxx)	Arm 5 (N=xxx)
n	xxx	xxx	xxx	xxx	xxx
Responder [1]	xxx (xx%)				
Non-Responder	xxx (xx%)				
CIS Arm v Arm 5					
Adjusted Odds Ratio	x.xx	x.xx	x.xx	x.xx	
95% C.I.	(x.xx, x.xx)	(x.xx, x.xx)	(x.xx, x.xx)	(x.xx, x.xx)	
p-value	x.xx	x.xx	x.xx	x.xx	

[1] Responder is defined as an ASUI total score  $\geq 0.09$  points increase from baseline.

Note: The analysis method was logistic regression adjusted for randomised treatment arm, baseline ASUI total score, country, gender and age

Example : EFF\_T4

Protocol : 207040

Population: Intent-to-Treat

Page 1 of 1

Table 2.xx

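### The annualised severe exacerbation rate is an unweighted mean of individual ratios, so one early event with an early stop can supply much of an arm's figure

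*SAP*

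**What the plan says.** In SAP 7.3.2.2, under the summary for the annual rate of severe exacerbations, "the annualized rate of severe asthma exacerbations for the ITT population will be calculated for each participant as" the quotient "the number of exacerbations / time on Relvar/Breo (in years) from randomisation". The unit of calculation is the participant, not the arm. Counted events run from randomisation to the day after exposure stops, or to study discontinuation if that is earlier.

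SAP 10.5.2 converts exposure to years as "Last treatment stop date - Randomisation Date + 1 / 365.25", to be read with the evident bracket around the day count. It sets no minimum exposure.

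Mock shell EFF_T15 in SAP Appendix 9 shows the rate for each arm as n, mean, SD, median, minimum and maximum. It shows no confidence interval and no weighting by time. The same shell has rows for the total number of events and for participants whose exacerbations led to withdrawal from the study. The exposure shell (Table 1.38) has a row for total subject-years. The SAP never divides one total by the other.

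**The concern.** Averaging individual rates gives each participant the same weight, whether he or she was observed for one week or for 24. A short denominator turns a single event into a very large personal rate, and that rate enters the arm mean at full weight.

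The denominator can also depend on the numerator. If an exacerbation leads someone to stop Relvar/Breo, the clock stops soon after the event, and the ratio is large because the event happened. EFF_T15 provides for this case by counting exacerbations that led to withdrawal. The result would be an arm figure, shown side by side for five arms, that depends heavily on whether one or two participants stopped early after an event.

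**Working it through.** **Inputs from the documents.** The documents state no exacerbation rate, so there is no planned figure for this endpoint to reproduce. Arm size comes from Protocol 11.2.1: "Approximately 432 patients will be randomised in order to obtain at least 380 subjects (i.e. 76 subjects per arm) with available data". With 12% dropout, 380/0.88 = 431.8, which reproduces 432. Allocation is equal over five arms, so 432/5 = 86.4, about 86 per arm. "The treatment period for the study is 6 months" (Protocol 5.1), and SAP Table 5 ends Month 6 on Day 168.

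**Assumptions.** The number of other events in the arm (10, 20 or 40, all in 168-day completers), the true event rate, and the share of events that end treatment are not in the documents. Ranges are shown.

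**One participant's effect.** With one event and exposure ending on day d, the personal rate is 365.25/d, and it adds (365.25/d)/86 to the arm mean. In total events over total person-years it adds 1/[(85 × 168 + d)/365.25]. A completer with one event has 365.25/168 = 2.17 per year.

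| Stop day | Personal rate per year | Added to mean of ratios | Added to events over person-years |
|---|---|---|---|
| 7 | 52.2 | 0.61 | 0.026 |
| 14 | 26.1 | 0.30 | 0.026 |
| 28 | 13.0 | 0.15 | 0.026 |

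**Share of the arm mean.** With b other events, the rest of the arm contributes b × 2.17/86. For b = 10 this is 0.253. Adding 0.303 for a day-14 stop gives 0.556, and 0.303/0.556 = 55%. The pooled rate moves only from 0.253 to 11/39.1 = 0.281.

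| Other events | Day 7 | Day 14 | Day 28 | Share of pooled rate |
|---|---|---|---|---|
| 10 | 71% | 55% | 38% | 9% |
| 20 | 55% | 38% | 23% | 5% |
| 40 | 38% | 23% | 13% | 2% |

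**Withdrawal unrelated to events.** Both estimators are unbiased. For a constant rate, the variance of the mean ratio is proportional to E[1/T] and that of the pooled rate to 1/E[T], so their ratio is E[1/T] × E[T] and does not depend on the rate. Take 12% stopping uniformly on days 1 to 84 and the rest at day 168:
- E[1/T] = 0.88/168 + 0.12 × 0.0597 = 0.0124, where 0.0597 is the mean of 1/d over days 1 to 84.
- E[T] = 0.88 × 168 + 0.12 × 42.5 = 152.9.
- Ratio = 0.0124 × 152.9 = 1.9.

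Simulation SDs give (0.168/0.130)² = 1.7 at 0.6 per year and (0.222/0.169)² = 1.7 at 1.0. At 0.3 they give (0.155/0.089)² = 3.0. Because the ratio does not depend on the rate, I read that as simulation noise from the heavy tail.

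**Events that can end treatment.** Arms of 86 with 168 days of follow-up and an assumed 0.5 per year were simulated. If 10% of events end treatment, the mean ratio averages 0.74 to 0.75 with a 1-day exposure floor, about 0.65 with 7 days and about 0.63 with 14 days; the median simulated arm is about 0.59. If 2% do, it averages 0.53 to 0.54. The pooled rate stays at 0.50. The plan's day count cannot fall below 1, so the 1-day floor is the plan as written; the longer floors show how much the average owes to events in the first days. With 12% dropout added and 10% of events ending treatment, true rates of 0.3, 0.6 and 1.0 gave 0.40, 0.81 and 1.33 for the mean ratio, against 0.30, 0.60 and 1.00 pooled.

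**The case against.** The strongest reply is that nothing inferential uses this figure. The endpoint sits under exploratory health care utilisation, its method is a summary, and EFF_T15 has no between-arm difference, interval or p-value for it. That stands. A reader might infer that the trial's conclusions, or a planned arm comparison of exacerbation rates, are undermined; the documents do not support this, because no such comparison or test is planned.

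A second reply is that the tables expose the problem. The maximum would show a value of 26 per year, events leading to withdrawal are counted, and a reader could divide total events by total subject-years from two displays. This is partly right, but the pooled rate is not printed, has no interval, and has to be assembled across tables. The median does not help. At 1.0 per year over 168/365.25 = 0.46 years, the expected share with any event is 1 − exp(−0.46) = 37%, below half, so the median would be 0.

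A third reply is that the size rests on assumptions, and it does. A reader might infer that the upward bias is certain, or that its size is known. The documents give neither a rate nor a share of events ending treatment, and Protocol section 8 does not list an exacerbation as a withdrawal criterion. Amendment 01 also reports dropout well below expectation. With 2% early dropout the variance ratio falls to (0.98/168 + 0.02 × 0.0597) × (0.98 × 168 + 0.02 × 42.5) = 1.16. Fewer early stops make the problem less likely, but they do not reduce the weight of one such case.

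**Conclusion.** The point holds as a defect of estimation in a named exploratory endpoint. The plan's rule gives one event with a day-14 stop about 12 times the weight of the same event in a completer (26.1 against 2.17 per year). That participant supplies about a quarter to a half of the arm mean when 10 to 40 other events occur.

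The extra variance, about 1.7 to 2 times, needs only unrelated early dropout at the planned 12%. The upward bias needs events that end treatment: at an assumed 0.5 per year, it is 0.03 to 0.04 per year if 2% do and about 0.13 to 0.25 if 10% do. These results assume a constant event rate and 86 per arm. No test, and no primary or secondary conclusion, depends on them. The change is worth making because the planned figure is labelled an annualised rate and will be read as one.

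**What to change.** In SAP 7.3.2.2 and shell EFF_T15, define the annualised rate for each arm as total on-treatment severe exacerbations divided by total person-years on Relvar/Breo, with a 95% CI and a statement of how the interval allows for repeat events in one participant. The individual rates may stay in a listing. A negative binomial model with log time as offset is optional.

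Two definitions should be settled in the same edit. The event window runs one day past the end of exposure while the denominator does not. The handling of missing event dates also differs: the EFF_T15 footnote keeps only events with both dates, SAP 10.5.3.3 imputes missing dates, and SAP 10.6.3 treats exacerbations like adverse events, whose missing dates are not imputed. These need to be reconciled, because they decide which events enter the numerator.

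The cost is SAP and shell wording and a few lines of programming. No new data are needed.
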